3.3 REGISTRY EXITS

Once a subject is enrolled and successfully implanted, every effort should be made to continue to follow the subject in the registry. However, it is inevitable that some subjects will decline to participate further, change geographic location, or become non-compliant with the visit schedule.

3.3.1 Withdrawal of Consent

If consent is withdrawn, obtain the date of withdrawal and reason for withdrawal of consent, then complete a Registry Exit eCRF.

3.3.2 Subject Death

In the event of subject death during registry participation, personnel at the investigational site are asked to notify BIOTRONIK as soon as possible by completing an Out of Service and Registry Exit eCRF. If subject death was associated with an adverse event, an Adverse Event eCRF will also be required.

The following information should be reported for any subject death:

- Death certificate or death report, signed by the investigator, that includes:
 - o Date and time of death
 - o Place death occurred
 - o Identification of the rhythm at the time of death, if known (include any available documentation)
 - o Immediate cause of death
 - o Any other circumstances surrounding the death
 - o Whether death was device or procedure related

-
- Timing for Institutional Review Board (IRB) or Ethics Committee (EC) notification (if required by the IRB/EC)
 - Protego lead return status

Whenever possible, devices that are explanted must be returned to BIOTRONIK for analysis.

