4.2 CLINICAL EVENTS COMMITTEE

A Clinical Events Committee (CEC) consisting of at least 3 independent electrophysiologists will be established to review and adjudicate adverse events that occur during the registry. The CEC will be blinded to the clinical registry site and subject identity, and to minimize bias, members will not participate as investigators. The CEC will create a registry specific charter defining the adverse event adjudication process, specifically detailing review guidelines along with appropriate response timelines.

All protocol defined adverse events included in the primary and secondary endpoint analysis (see Section 10.3.1 and Section 10.3.2) will be adjudicated by the Clinical Events Committee. The Clinical Events Committee (CEC) will have the responsibility to adjudicate the classification and category of each reported adverse event. In addition, the CEC will also indicate whether the adverse event is related, possibly related, not related, or has an unknown relation to the Protego lead.

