6. RISKS AND RISK MINIMALIZATION

All devices included in this registry are legally marketed and being prescribed by physicians according to FDA approved indications for use.

As with any implantable device, there are always potential risks that accompany the device. The following list provides the potential risks that may occur with the Protego DF4 lead in combination with an ICD or CRT-D device.

- Acceleration of arrhythmias
- Air embolism
- Allergic reactions to contrast media
- Arrhythmias
- Bleeding
- Body rejection phenomena
- Cardiac tamponade
- Chronic nerve damage
- Damage to heart valves
- Damage to lead during implant procedure
- Device migration
- Elevated pacing thresholds
- Embolism
- Erosion or pocket erosion
- Extrusion
- Fluid accumulation
- Hematomas, cysts, or fibrotic tissue
- Incomplete lead connection with the pulse generator
- Infection
- Inappropriate detection of ventricular arrhythmias
- Inappropriate therapy, including inappropriate shocks
- Keloid formation
- Lead abrasion and discontinuity
- Lead migration / dislodgment
- Lead fracture / insulation damage
- Lead perforation
- Lead-related thrombosis

-
- Local tissue reaction / fibrotic tissue formation
 - Muscle or nerve stimulation
 - Myocardial damage
 - Myopotential sensing
 - Pacemaker mediated tachycardia
 - Pneumothorax
 - Potential death due to inability to defibrillate or pace
 - Psychological effects (dependency, depression, fear of premature battery depletion, fear of shocking while awake, fear that shocking ability may be lost, anxiety about device resulting from frequent shocks, imagined (phantom) shock)
 - Random component failure
 - Shunting current or insulating myocardium during defibrillation with internal or external paddles
 - Thromboembolism
 - Undersensing of intrinsic signals
 - Valvular damage
 - Venous occlusion
 - Venous or cardiac perforation
 - Ventricular ectopy

These risks can be minimized through use of strict aseptic technique, compliance with the registry protocol and technical implant procedures, adherence to the guidelines for selection of subjects, close monitoring of the subject's physiologic status during the implant and follow-up procedures, and by promptly supplying BIOTRONIK with all pertinent information required by this protocol.

BIOTRONIK foresees no additional risks associated with this registry beyond those stated in the labeling for the respective pulse generators and leads.

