10.2 ENDPOINT ANALYSIS

All protocol defined adverse events included in the primary and secondary endpoint analysis will be adjudicated by the Clinical Events Committee (CEC) (see Section 2.1). The CEC will have the responsibility to adjudicate the classification and category of each reported adverse event as implant procedure, implanted pulse generator, lead, or non-procedure non-system related. For each adverse event, the CEC will indicate whether the adverse event relatedness to the Protego lead is: not related, related, possibly related, or unknown.

In evaluation of the two primary endpoints for the post-approval registry, the estimates of AE rates will be based on the number of subjects with at least one "related" AE as a proportion of total subjects. Subjects with a final adjudicated related AE classification of "possibly related", "not related" or "unknown" will not have that individual event contribute to or be included in the evaluation of primary safety endpoints. The same rules will be used for purposes of Kaplan-Meier survival analyses, described in Section 2.4.2.

Secondary endpoint 3, which includes AEs that were excluded from primary safety endpoint 1 through 5 years post-implant, will also be summarized as AE rates along with their associated, exact 95% confidence intervals.

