10.3 ADVERSE EVENTS FOR THE ANALYSIS OF THE PRIMARY AND SECONDARY ENDPOINTS

10.3.1 Adverse Events for the Analysis of Primary Endpoints 1 and 2

If any of the following invasive actions occur in order to resolve an above listed Protego lead-related AE, the AE will be included in the primary safety endpoint analysis:

- Lead surgically repositioned
- Lead surgically explanted
- Lead surgically replaced
- Lead surgically abandoned
- Other lead-related surgery performed

Additionally, if any of the following non-invasive actions occur in order to resolve an above listed Protego lead-related AE, the Protego lead-related AE will be included in the primary endpoint analysis:

- Lead pacing polarity or pacing mode reprogrammed due to suspected lead failure.
- Lead abandoned and pacing disabled due to clinical failure or suspected lead failure
- Lead use continued based on medical judgment despite a known clinical failure or suspected lead failure

AEs that are corrected by reprogramming the pulse generator (other than the above) and resolved without invasive action will not be considered an adverse event counted towards the primary endpoints. For example, electrical reprogramming of the pacing polarity to eliminate extra-cardiac stimulation will not be considered an adverse event. Similarly, increasing pacing output as a result of an elevated threshold without further intervention does not count toward the primary endpoint analysis.

Subject deaths as a result of a Protego lead-related AE will be included in the primary endpoint analysis.

Primary endpoints 1 and 2 will exclude 1) lead dislodgements that occur within 30 days after lead implant or a lead revision procedure and 2) high pacing threshold, intermittent capture, no lead capture within 30 days after lead implant or a lead revision procedure. However, these will count towards the adverse event secondary endpoint.

In addition, the following two pulse generator-related adverse events will be included in the analysis of primary endpoints 1 and 2: DF4 header connector malfunction and DF4 header fluid intrusion.

10.3.2 Adverse Events for the Analysis of Secondary Endpoint 3

If any of the following invasive actions occur in order to resolve an above listed RA or LV lead-related AE, the AE will be included in the secondary endpoint analysis:

- Lead surgically repositioned
- Lead surgically explanted
- Lead surgically replaced
- Lead surgically abandoned
- Other lead-related surgery performed

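### Deaths from lead failure count in the primary endpoints, but a death reaches independent adjudication only if the site first links it to an adverse event

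*Combined protocol and SAP*

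**What the plan says.** Lead-related deaths belong in the primary endpoints. Section 10.3.1: "Subject deaths as a result of a Protego lead-related AE will be included in the primary endpoint analysis". Section 6 lists the clinical scenario as a known risk: "Potential death due to inability to defibrillate or pace".

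For every death, Section 3.3.2 asks the site to "notify BIOTRONIK as soon as possible by completing an Out of Service and Registry Exit eCRF". An AE form is conditional: "If subject death was associated with an adverse event, an Adverse Event eCRF will also be required". The investigator-signed death report must also cover rhythm at death if known, immediate cause, circumstances, and "Whether death was device or procedure related". The return status of the lead is reported as well.

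Section 4.2 says the CEC "will be established to review and adjudicate adverse events that occur during the registry". What it adjudicates is stated in the same section: "All protocol defined adverse events included in the primary and secondary endpoint analysis". Section 10.2 repeats this and adds that only events finally rated as related count in the primary endpoints. Events rated possibly related, not related or unknown do not.

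Section 2.3.1 includes death in the assumed loss to follow-up. Section 2.4.3 restricts the primary hypothesis tests to subjects who reach 5 years or have an AE before then, with no imputation. In the Kaplan-Meier analyses, follow-up is censored at withdrawal or the last completed visit.

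**The concern.** The plan intends to count deaths caused by the lead but makes their detection depend on the site's own referral. Failure to deliver a shock or to pace may show itself only as sudden death. It also falls within the Summary's stated purpose of characterising lead failures that contribute to loss of bradycardia or shock therapy.

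If the site sees no link to an AE, no passage sends the case to the CEC. Section 4.2 blinds the committee to site and subject and keeps investigators off it to limit bias, yet for these deaths the investigator decides whether the committee sees the case at all. The Kaplan-Meier monitoring in Section 2.4.2, which triggers reports to FDA, uses the same counting rules (Section 10.2) and would miss the same deaths.

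An unreferred lead death can only make the lead look safer. It cannot add a false event.

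**Working it through.** **Route of a death through the plan**

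| Step | AE form filed | No AE form filed |
|---|---|---|
| Forms (3.3.2) | Out of Service, Registry Exit, AE | Out of Service, Registry Exit |
| CEC review (4.2, 10.2) | Yes, for AEs in the endpoint analyses | None stated |
| Binomial tests (2.4.3, 10.2, 10.3.1) | Event if rated related | Subject excluded if death precedes 5 years and there was no earlier AE |
| Kaplan-Meier (2.4.3, 10.2) | Event if rated related | Censored |

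Death itself is on none of the reportable AE lists in Section 10.1. The returned-product results in Section 2.1.4 are additional data and are not tied to adjudication.

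**Reproducing the plan's figures**

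Inputs from Sections 2.3 and 2.4.1: exact binomial test, one-sided alpha 0.025, goal 92.5%, assumed AE-free rate 95.0%; for endpoint 2, an exact two-sided 95% upper bound below 1%.

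- Endpoint 1, n = 750: the largest c with P(X ≤ c | 750, 0.075) ≤ 0.025 is c = 42. The attained alpha is 0.0247 and the power, P(X ≤ 42 | 750, 0.05), is 0.801. The plan's 750 reproduces.
- Attrition: 750/0.9^5 = 1270.1, rounded up to 1271; 1000/0.9^5 = 1693.5, rounded up to 1694. Both reproduce.
- Exits allowed, deaths included: 1694 × (1 − 0.9^5) = 693.7, about 694.
- Endpoint 2, n = 1000: the exact upper bound is 0.87% at 3 events (pass) and 1.02% at 4 (fail). The assumed 0.4% is 4 in 1000, so it meets 1% only after rounding.

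**Tipping points**

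Let k be the number of missed lead deaths, an assumption. Each adds one event and one subject, because these subjects are otherwise outside the binomial set. The exact upper bound for x events in n is the 97.5th percentile of Beta(x + 1, n − x), evaluated at x + k events in n + k subjects.

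| Endpoint | Observed | k | With k added | Upper bound | Limit | Result |
|---|---|---|---|---|---|---|
| 1 | 38/750 | 0 | 38/750 | 6.89% | 7.5% | pass |
| 1 | 38/750 | 4 | 42/754 | 7.46% | 7.5% | pass |
| 1 | 38/750 | 5 | 43/755 | 7.60% | 7.5% | fail |
| 1 | 50/1000 | 9 | 59/1009 | 7.48% | 7.5% | pass |
| 1 | 50/1000 | 10 | 60/1010 | 7.58% | 7.5% | fail |
| 2, one AE type | 3/1000 | 1 | 4/1001 | 1.02% | 1% | fail |
| 2, one AE type | 0/1000 | 4 | 4/1004 | 1.02% | 1% | fail |

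The observed counts for endpoint 1 are the plan's assumed 5% event rate applied to 750 and to 1000 evaluable subjects (37.5, rounded to 38, and 50).

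**The case against.** - **The trigger is wider than it may look.** Section 3.3.2 does not require the AE to precede death or to have been recognised in life. A lead fault found at or after death, in stored data, Home Monitoring or the returned lead, fits the wording. Undersensing and lead failure are listed in Section 10.1.3. A reader might infer that a lead death counts only if the lead problem was known beforehand; the text does not say so. This stands, and it confines the gap to deaths that the site does not connect to any AE.
- **The CEC does rate relatedness.** Once an AE form exists, the committee makes the final rating. The site controls referral, not the outcome. This stands.
- **Section 10 defines an AE broadly enough to include death.** It might, but Section 3.3.2 treats an AE as something a death may or may not be associated with. At best the sections are ambiguous and sites will differ.
- **Other safeguards exist.** Monitoring covers the reporting of deaths (Section 7.1), root causes of failures are investigated (Section 2.4.2), explanted devices are returned where possible (Section 3.3.2), and Home Monitoring sends daily data. These lower the risk, but none is independent adjudication.
- **The CEC charter may require death review.** It is not among the documents. The protocol does not require it to do so.
- **Review alone would barely move the result.** A subject found dead with rhythm unknown may well be rated unknown, which Section 10.2 excludes. This stands, and is why the fix needs a sensitivity analysis.

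**Conclusion.** The gap is real on the text and runs in one direction: a sudden or unexplained death that the site does not link to an AE has no required independent review, although lead-related deaths are primary events.

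Two stronger readings fail. A reader might infer that such subjects are scored as event-free successes in the primary test. They are not: Section 2.4.3 excludes them, and only Kaplan-Meier carries them as event-free up to censoring. A reader might also infer that the gap probably changes the main result. The documents give neither a death rate nor a share of sudden deaths, so the bias cannot be sized, and up to four missed deaths leave endpoint 1 passing at 38/750.

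What can be stated are tipping points: five missed deaths for endpoint 1 at 38/750, ten at 50/1000, and one for an endpoint 2 type with 3/1000. They rest on the plan's assumed 5% rate for endpoint 1 and on illustrative counts for endpoint 2. They also assume that every missed death would have been rated related. The endpoint 2 figures further require all the missed deaths to fall in the same AE type, and Section 2.3 describes that comparison as non-powered. The sample size itself is not in question. The change is worth making because it is cheap and the failure mode is among the most serious for this device.

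**What to change.** In Sections 3.3.2 and 4.2, and in the CEC charter, require that the following go to the existing CEC whether or not an AE form exists:

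- every death that is sudden, unwitnessed, arrhythmic, or of unknown cause or rhythm;
- every death the site marks as device- or procedure-related.

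Each case should carry the death report already required, available interrogation or Home Monitoring data, and any returned-lead analysis. The CEC then rates relatedness to the Protego lead.

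Count deaths rated related in endpoints 1 and 2. Add a pre-specified sensitivity analysis that counts deaths rated possibly related or unknown as events, entering each in both numerator and denominator, and report how many there are.

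Cost: wording changes, some additional CEC workload, and possibly a slightly higher primary event count. No new visits or data collection from subjects are needed.

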3.3.3 Protego Lead or Pulse Generator Extraction

Any subject who has the Protego lead explanted or capped, and is not implanted with another Protego lead, will be withdrawn from the registry. Additionally, any subject who has their BIOTRONIK pulse generator explanted and replaced with a non-BIOTRONIK device will also be withdrawn from the registry (even if the Protego lead remains). Only complete a registry exit eCRF after documentation of the system revision procedure (see Section 3.2.5.2) is available. For example, if the Protego lead and pulse generator are explanted due to infection, the subject should not be exited until a non-registry lead/system is implanted or documentation is available stating that the subject will not be re-implanted with a registry qualifying lead/system. Report the exit on the Registry Exit eCRF and any adverse events resulting from the explant procedure.

Whenever possible, devices that are explanted must be returned to BIOTRONIK for analysis.

3.3.4 Lost to Follow-up

Subjects lost to follow-up are those for whom contact is lost despite the investigator's best efforts to locate the subject. Registry sites should attempt to contact these subjects in order to maintain registry visit compliance and all contact attempts should be documented. At a minimum, the site should make and document two attempts to contact the subject by phone and one attempt by certified mail.

In the event the subject cannot be contacted using the above methods, the subject should be exited from the registry by completing a Registry Exit eCRF.

3.3.5 Registry Participation Complete

All subjects are expected to be followed for a minimum of 59 months accounting for the visit expectation of 60 months (5 years) \pm 1 month. After a subject completes their final routine visit in this time interval, their study participation is complete and the subject should be exited from the registry by completing a Registry Exit eCRF.

4. REGISTRY ORGANIZATION

4.1 SPONSOR

BIOTRONIK is the sponsor of the Protego DF4 post-approval registry. A sponsor is defined as an entity that initiates but does not conduct an investigation. BIOTRONIK's responsibility as the clinical registry sponsor is to ensure protocol and regulatory compliance through proper monitoring of the investigation. BIOTRONIK is required to ensure that the registry device is used under the immediate direction of an investigator.

4.2 CLINICAL EVENTS COMMITTEE

A Clinical Events Committee (CEC) consisting of at least 3 independent electrophysiologists will be established to review and adjudicate adverse events that occur during the registry. The CEC will be blinded to the clinical registry site and subject identity, and to minimize bias, members will not participate as investigators. The CEC will create a registry specific charter defining the adverse event adjudication process, specifically detailing review guidelines along with appropriate response timelines.

All protocol defined adverse events included in the primary and secondary endpoint analysis (see Section 10.3.1 and Section 10.3.2) will be adjudicated by the Clinical Events Committee. The Clinical Events Committee (CEC) will have the responsibility to adjudicate the classification and category of each reported adverse event. In addition, the CEC will also indicate whether the adverse event is related, possibly related, not related, or has an unknown relation to the Protego lead.

5. DATA COLLECTION

5.1 ELECTRONIC DATA CAPTURE (EDC)

MedNet Solutions Incorporated is a privately held company that specializes in web-based clinical data management technology. MedNet will host the EDC system and provide a secure environment that is accessible to authorized individuals through the internet. BIOTRONIK will implement a registry specific configuration using this software to meet the data collection requirements of the protocol. The EDC system is 21 CFR Part 11 compliant and is the platform for electronic case report form (eCRF) data entry, clinical data discrepancy resolution, and access to reports for BIOTRONIK, specified investigational sites, and any other parties authorized by BIOTRONIK.

5.2 CASE REPORT FORMS (CRFs)

Original data will be collected at each investigational site and recorded into the EDC system, audited and monitored by BIOTRONIK, via completion of electronic CRFs (eCRFs). The investigator will be required to use an electronic signature to approve the content of the data reported in the eCRFs.

Information from electronically delivered source data (e.g. programmers) will be captured and stored in a validated environment until the end of the registry.

Subject follow-up is required for all subjects enrolled in this clinical registry. The required follow-up visit dates are based on Protego lead implant date, and are to be used for the calculation of the dates of the routine follow-up schedule. The following eCRFs will be available in the EDC system:

- Informed Consent
- Enrollment
- Implant Procedure
- Implant Test Values
- Routine Follow-ups (\pm 30 days)
- Unscheduled Interim Follow-up
- Adverse Event
- System Revision
- Out of Service
- Registry Exit
- Protocol Noncompliance
- Data Clarification

5.3 DATA CLARIFICATION/DATA QUALITY CONTROL

BIOTRONIK will review registry data. At any time, reports can be generated on data completion and missing data for each investigational site. An EDC system will be used to track received and expected follow-up data and eCRFs for each participant. This system provides the capability to monitor the status, volume, and disposition of data as well as to identify data completed, due, overdue, and backlogged. In addition, all registry data will undergo extensive automatic edit and plausibility checks which provide information to the investigational sites to help improve and maintain data quality control procedures designed to detect inaccuracies and inconsistencies.

To ensure protocol compliance at all participating investigational sites, BIOTRONIK monitors will conduct monitoring visits (see Section 7).

To ensure compliance with federal regulations, internal policies and procedures, and the registry protocol, the EDC vendor will also be monitored and/or audited by BIOTRONIK or a BIOTRONIK representative during the course of the registry.

